5.2.1 Concomitant medications will be documented on the Case Report Form (CRF)

Patients will receive full supportive care including transfusion of blood and blood products, antibiotics, and anti-emetics, when appropriate. The reason(s) for treatment, dosage and the dates of treatment will be recorded:

- Prescription medications
- Over the counter medications

- Herbal treatments/nutritional supplements
- Other blood products

5.2.2 Plasma Collection

Donors will be screened using FDA/American Red Cross (ARC) policies, as detailed in section 6.0. Two units of donor-directed plasma units will be collected by ARC or local donation site via FDA Emergency Use Authorization from donors identified to have recovered from COVID-19 28 days or later after symptom resolution. Appropriate donor screening with one lavender top tube for ABO, HLA and infectious disease screening per ARC or local center standard will be performed. If the units are cleared and identified for transfusion, the directed donor will be sent to the ARC or other local donation site for plasmapheresis on day 28 or later after the symptom resolution. The appropriate identifiers will be verified at the blood bank and at the bedside per standard transfusion procedures.

5.2.3 Steroids/other therapy

Steroids for the treatment of reactive airway disease and/or pneumonia are allowed as well as steroids for anti-emetic regimen, adrenal failure, septic shock, pulmonary toxicity or hormones administered for non-disease-related conditions (e.g. insulin for diabetes). High dose steroids are discouraged but steroid use is left to the judgement of the attending physician team.

5.2.4 Acceptable Concomitant Medications

All treatments that the investigator considers necessary for a subject's welfare may be administered the discretion of the investigator. All concomitant medication including all prescription, over-the-counter (OTC), herbal supplements, and IV medications and fluids will be collected from the medical record.

5.2.5 Prohibited Concomitant Medications

Subjects are prohibited from receiving medications or vaccinations that are specified in the exclusion criteria during study treatment.

5.2.6 Subject Removal

Subjects should be removed from the trial if they require >6L/min supplemental oxygen or mechanical ventilation prior to receiving convalescent plasma infusion. Subjects may receive other medications that the investigator deems to be medically necessary.

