4.0 ELIGIBILITY

4.1 Inclusion Criteria for Enrollment as a Plasma Recipient

- Patients must be 18 years of age or older
- Patients hospitalized with COVID-19 respiratory symptoms and confirmation via SARS-CoV-2 RT-PCR testing.

- Patient positive for COVID-19 with respiratory symptoms within 72 hours of admission (not in ICU or on high flow oxygen)
- Patient or surrogate is willing and able to provide written informed consent and comply with all protocol requirements.
- Patients with hematologic malignancies or solid tumors are eligible.
- Patients with autoimmune disorders are eligible.
- Patients with immunodeficiency or organ or stem cell transplant are eligible.
- Patients who have received or are receiving hydroxychloroquine or chloroquine are eligible (will be taken off the drug at enrollment)
- Prior use of IVIG is allowed but the investigator should consider the potential for a hyper-coagulable state

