4.3 Control Group (obtained via chart review and includes control specimens)

Inclusion Criteria:

1. Admitted to a “floor” bed (non-ICU bed) at UVAMC on/after March 30, 2020 due to confirmed COVID-19 disease
2. Age \geq 18 years of age

Exclusion Criteria:

1. Requiring mechanical ventilation or >6 liters per minute nasal cannula upon admission
2. Participation in other interventional anti-COVID-19 treatment trials
3. Medical conditions for which receipt of 200-400mL of intravenous fluid may be dangerous to the subject (e.g. decompensated congestive heart failure)
4. Receipt of convalescent immune plasma for treatment of COVID-19

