5.2.7 Enrollment, Screen Failures, and Study Completion

Patients are considered enrolled from time consented to participate until designated as a screen failure or have either been discontinued from the study or completed it. A screen failure is a patient who signed informed consent, but then was determined to be ineligible or withdraws from the study. Subjects are considered to have completed the study when they are followed through day 60 or have had an adverse event or death occurred prior to day 60.

Day -1 to 0 Baseline:

- A. Subject informed consent (obtained before performing study related activities)
- B. Baseline Evaluation at screening.
 1. Demographics (Age, sex ethnicity, race)
 2. Medical history (timing of exposure to COVID-19 source patient, acute and chronic medical condition, medications, allergies.) Any medical condition arising after consent should be recorded as AE.
 3. COVID-19 symptom screen (fevers, cough, shortness of breath, diarrhea, anosmia), onset of symptoms, source of contagion
 4. Vital signs

5. COVID-19 testing (RT-PCR) from nasopharyngeal, throat, tracheal aspirate or bronchoalveolar lavage and stool (optional) samples
6. Blood typing, CBC with differential, comprehensive metabolic panel
7. Serological testing: anti-SARS CoV-2 titers
8. Immune testing samples
9. Urine or serum pregnancy test for females of childbearing potential. Results from laboratory tests obtained up to 7 days before enrollment may be used for the pregnancy test.
10. Determination of eligibility as per inclusion/exclusion criteria, age, consent, positive for COVID-19, respiratory symptoms within 72 hours of admission

DAY 0 Baseline and Infusion:

1. Study Plasma Administration: 1-2 units of plasma will be transfused over 1-2 days. Time at start and end of infusion will be recorded and vital signs will be measured immediately prior to infusion, 10-20 minutes after start of infusion, at completion of infusion and 30-60 minutes after the end of the infusion
2. COVID-19 symptom screen (fevers, cough, shortness of breath)
3. Assessment of clinical status (8-point ordinal scale)
4. New medical conditions, concomitant medication, AE evaluation
5. Physical examination
6. COVID-19 testing (RT-PCR) from nasopharyngeal, throat or stool (optional) samples
7. Blood typing, CBC with differential, comprehensive metabolic panel, C-reactive protein
8. Serological testing: anti-SARS CoV-2 titers

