7.0 STATISTICAL CONSIDERATIONS

7.1 Statistical Analyses

Twenty-nine evaluable patients will have 80% power to declare a significant decrease in ICU admissions from a historical control of 50% of hospitalized patients to 25% with a two-sided type I error of 0.05 (reject ICU admission rate=50% if only 8 or less patients are admitted to ICU among 29 evaluable patients). The historic control group will consist of 29 patients who are gender and age (within 5 years) matched.

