9.0 STATISTICAL CONSIDERATIONS

9.1 Power calculation

Twenty-nine evaluable patients will have 80% power to declare a significant decrease in ICU admissions from a historical control of 50% of hospitalized patients to 25% with a two-sided type I error of 0.05 (reject ICU admission rate=50% if only 8 or less patients are admitted to ICU among 29 evaluable patients).

Data analysis: For categorical clinical endpoints, frequency with percentage will be summarized. For the quantitative clinical variables and immune response variables measured in this objective, we will produce summary statistics (including means, medians, and standard deviations) for data at pre- and post-CIP infusions. Subsequent analyses will compare the serologic and neutralization antibody titers for anti-SARS-COV-2 antibodies and immune response variables (after a suitable data transformation to improve normal distribution, if necessary) pre- and post-treatment using a paired t-test (or Wilcoxon sign ranked test if the data are not approximately normally distributed). The level of each measured immune biomarker measured at the follow-up time points will be plotted to visually show the change of immune responses over time. To explore whether immune responses at pre- or peak improvement at post-CIP infusions associate with clinical endpoints (such as ICU admission, intubation), logistic regression for binary endpoints and Cox regression for time to event endpoints will be used to analyze each measured immune biomarker respectively. These effects will be compared to biospecimen from non-transfused immunologic controls. Analyses will adjust for other covariates such as age and co-morbidities. No

multiplicity adjustment is planned due to the nature of being exploratory. A two-sided p-value of < 0.05 will be considered significant.

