10.9 Subject Status Definitions

- Enrolled: All subjects who sign an informed consent will be considered enrolled on the study. All subjects consented on the study must be entered into Clinical Trials Office Database.
- Screen Failure: A subject who is withdrawn or discontinues from study screening prior to being on study is considered a screen failure. Screen failures are not considered a study accrual and will be replaced. Note: The IRB defines any individual that has signed an informed consent as an enrollment in this study and so screen failures should be reported to the IRB with enrollment numbers.
- On-Study: A subject is considered on-study on the date when the study team has confirmed the subject has met all of the inclusion and none of the exclusion criteria, and the treating physician/surgeon or study PI has signed off on the confirmation.
- On-Treatment: A subject is considered on-treatment on the date that they receive the first study treatment. A subject who is withdrawn or discontinues from the study after receiving at least 1 infusion is considered a discontinuation and will not be replaced.
- On Follow-up: A subject is considered on follow-up on the date that they have met any of the criteria in section 4.0.
- Off-Study: A subject is considered off-study if they are removed from the study for any of the reasons listed in section 4.0 or if they have completed all study assessments through follow-up.
- Immunologic Controls: A subject for whom biospecimen is obtained from the COVID-19 Biorepository.

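### Recipients are selected on their status up to infusion, controls only on their status at admission and with no stated time zero, so the groups are not aligned for either primary endpoint

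*Combined protocol and SAP*

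**What the plan says.** **Recipients.** Section 4.1 admits patients within 72 hours of admission who are neither in the ICU nor on high flow oxygen. Section 5.2.6 adds: "Subjects should be removed from the trial if they require >6L/min supplemental oxygen or mechanical ventilation prior to receiving convalescent plasma infusion". Section 5.2.7 allows consent and screening on Day -1 to 0 and labels the next step "DAY 0 Baseline and Infusion", so a recipient's clock starts at infusion. Section 10.9 states: "Screen failures are not considered a study accrual and will be replaced".

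**Controls.** In 4.3 the respiratory exclusion is "Requiring mechanical ventilation or >6 liters per minute nasal cannula upon admission". The control list in the Summary has no oxygen limit. Section 7.1 adds: "The historic control group will consist of 29 patients who are gender and age (within 5 years) matched". No section gives controls an index time or requires them to be still on the floor at a time comparable to infusion.

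**Endpoints and rule.** The primary endpoints in 7.3.1 are ICU transfer and 28-day mortality, with no starting point for either. The decision rule in 7.1 and 9.1 is to "reject ICU admission rate=50% if only 8 or less patients are admitted to ICU among 29 evaluable patients". The 50% is described as a historical rate among hospitalised patients, without a source, and the term evaluable is not defined.

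**The concern.** Take two patients with the same course, each needing ICU care 30 hours after admission. If the first was heading for infusion at hour 36, that patient never becomes a treated recipient. The second, a control, met the limit at admission, stays in the group and counts as an ICU transfer. The reverse also happens: a patient who recovers and goes home before plasma can be given never becomes a recipient, but remains an event-free control.

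Both groups therefore come from floor admissions, but recipients are filtered by what happens up to the infusion hour and controls are not. Matching on age and gender does not touch this. The covariate adjustment in 9.1 does not either: it is described with the exploratory biomarker regressions and names age and co-morbidities. The fixed 50% has the same problem if it was counted from admission.

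The control group stands in for a placebo arm (3.2), so the efficacy reading depends on it. An inert product could look effective, or an effective one could be missed, because of who is left at the infusion hour.

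**Working it through.** **Step 1: the plan's own figures.** Inputs from 9.1: rates 0.50 and 0.25, two-sided 0.05, power 80%. The one-sample normal formula gives

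n = [1.960 × √(0.5 × 0.5) + 0.842 × √(0.25 × 0.75)]² / 0.25² = 28.92, so 29.

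The stated sample size reproduces (normal-approximation power 80.1%). Computed exactly, the 8-of-29 rule has P(X ≤ 8) = 0.012 at a rate of 0.50 and 0.71 at 0.25. These two values are the no-bias baseline below.

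**Step 2: a model of the misalignment.** Assume that 50% of floor admissions reach the ICU, counted from admission (the plan's rate; this origin is an assumption). Let f be the share of those ICU transfers that occur before the infusion hour, and d the share of the non-ICU patients discharged before it. The documents give neither. Those still eligible at the infusion hour are 0.5(1−f) who will go to the ICU and 0.5(1−d) who will not. With inert plasma the recipients' ICU rate is

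rate = 0.5(1−f) / (1 − 0.5f − 0.5d).

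If f = d the rate stays at 0.50. If f > d it falls and favours plasma; if d > f it rises and goes against plasma. Example: f = 0.4, d = 0 gives 0.30/0.80 = 0.375.

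**Step 3: consequences with inert plasma.** The third column is P(X ≤ 8) for n = 29 at the recipients' rate. The last column compares 29 recipients at that rate with 29 controls at 0.50. The plan names no test for this comparison, so a two-sided Fisher exact test at 0.05 is assumed and the matching is ignored.

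| f, d | Recipients' rate | Chance of meeting the 8-of-29 rule | Chance of significance favouring plasma (Fisher) |
|---|---|---|---|
| 0, 0 (or any f = d) | 50.0% | 0.012 | 0.012 |
| 10%, 0 | 47.4% | 0.024 | 0.021 |
| 20%, 10% | 47.1% | 0.026 | 0.022 |
| 30%, 20% | 46.7% | 0.029 | 0.023 |
| 20%, 0 | 44.4% | 0.048 | 0.034 |
| 40%, 20% | 42.9% | 0.068 | 0.044 |
| 40%, 0 | 37.5% | 0.18 | 0.098 |
| 20%, 40% | 57.1% | 0.001 | 0.003 (0.044 against plasma) |

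**Step 4: consequences if plasma halves the rate.** The chance of meeting the rule is 0.71 without bias (rate 25.0%), 0.55 with f = 20%, d = 40% (rate 28.6%), and 0.92 with f = 40%, d = 0 (rate 18.75%).

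**Not sized.** The documents give no death rate, so the effect on 28-day mortality cannot be computed. The mechanism is the same: recipients must survive to infusion, and nothing says when the 28 days start for controls.

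**The case against.** - **The assumed shares carry the size.** With mild values the 8-of-29 rule stays near its nominal lower-tail 0.025 (0.024 to 0.029 in the second to fourth rows), partly because the rule starts at 0.012. The 0.18 needs 40% of transfers before infusion and no early discharge. This stands: the size is unknown and could be small. It does not remove the gap, because nothing in the plan keeps f and d close.
- **The plan names no test against the controls.** Section 9.1 summarises categorical endpoints by frequency and percentage, and the only ICU rule is against a fixed 50%. True, so the Fisher column illustrates a comparison the plan says it will make without saying how. The fixed-rate test is exposed separately, through the unstated origin of the 50%.
- **Section 5.2.6 acts only between consent and infusion, and names oxygen and ventilation, not ICU transfer.** Correct. Much of the gap comes from the 72-hour entry window in 4.1. How an ICU transfer between consent and infusion is counted is not stated, and 10.9 does not clearly say whether a patient confirmed eligible and then removed is replaced. These gaps are reasons to define the analysis set.
- **Controls are also excluded for receiving plasma or joining other trials, which can follow admission.** True, but this does not align their respiratory status or their clock.
- **The control dates can be read together:** 4.3 gives a start (30 March 2020) and 3.2 an end (before the trial began). That reading is possible, but 4.3 itself has no end date and should state one.
- **This is a single-arm phase II trial with an openly chosen non-randomised comparator.** That excuses the lack of randomisation, not the lack of a common time zero.

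**Conclusion.** The concern holds. Followed as written, the plan compares recipients selected at the infusion hour with controls selected at admission, and may test the recipients against a benchmark counted from admission. Both primary endpoints are affected.

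The net direction cannot be read from the documents: it favours plasma if f exceeds d and goes against it if d exceeds f. In the scenarios shown, the chance that inert plasma meets the 8-of-29 rule runs from 0.001 to 0.18, against 0.012 without bias. The chance of success for a product that halves the rate runs from 0.55 to 0.92, against 0.71. These figures rest on the assumed f and d and on a 50% rate counted from admission. The existence of the misalignment rests only on the text. It should be corrected before the comparison is made.

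**What to change.** 1. **Sections 4.3 and 7.1.** Give each control a time zero equal to the matched recipient's hours from admission to the start of infusion. Require the control at that hour to be alive, still in hospital, outside the ICU, unventilated and at 6 L/min or less. Count ICU transfer and death for 28 days from that hour in both groups. Reconcile 7.2 (28 days of follow-up for the primary endpoints) with 9.2 (6 months).
2. **Sections 7.1 and 9.1.** Define evaluable. State the source of the 50% and put it on the same time origin. If that cannot be done, label the 8-of-29 test as subject to this bias, since step 1 alone does not repair it.
3. **Sections 4.3 and 3.2.** State an end date for the control window consistent with both sections, and state that anyone consented to this trial cannot be a control.
4. **Reporting.** Report patients removed before infusion, with their outcomes. Add a sensitivity analysis that keeps eligible, never-infused patients in the recipient group, counted from the on-study date, with controls aligned to that same point.

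The clinical removal rule in 5.2.6 is not changed.

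**Cost.** Protocol and SAP wording, plus admission, ICU, oxygen and discharge times from charts already under review. For recipients, 5.2.7 already provides: "Time at start and end of infusion will be recorded". Some candidate control charts will fail the condition at the matched hour and must be replaced; the documents do not give the size of the pool. Step 4 also needs outcome data on patients removed before infusion.

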2. Age \geq 18 years of age
3. No receipt of convalescent plasma

Immunologic Controls:

1. PBMCs with 5-10 million cryopreserved cells per specimen present in the prospective COVID 19 Biorepository
2. Serum or plasma 500 UI each from up to 50 patients present in the COVID-19 Biorepository

Assessment and Data Acquisition:

1. Baseline: Age, sex, comorbidities, date of symptom onset, known COVID-19 contact, type of admission to the floor or ICU, APACHE score (ICU scoring system to classify disease severity and mortality risk), SOFA score (mortality prediction score based on organ function), clinical status, vital signs including temperature, respiratory rate, oxygen saturation, oxygen requirement, neutrophil count, lymphocyte count, CRP, chest x-ray, chest CT, location in hospital.
2. Safety and efficacy: Day 0 (baseline), 1, 2, 3, 4, 7, 14, 21, and 28 and once at day 60.
3. SARS-CoV-2 PCR from OP or NP swabs: Day 0, 4, 7, 14 and at any time when there is clinical suspicion for COVID-19.
4. Outcome measures: increased O₂ requirement (PaO₂/FiO₂ ratio or SpO₂/FIo₂), supplemental oxygen strategy (nasal cannula, high flow nasal cannula, noninvasive ventilation, intubation and invasive mechanical ventilation, rescue ventilation i.e. neuromuscular blocking agents, prone positioning, corticosteroids, ECMO), vasopressors, renal support, ICU LOS, ICU mortality, hospital LOS, hospital mortality, 28 day mortality.
5. Serum or plasma antibody titer² to SARS-CoV-2: Day 0, 7, 14, and 28. Samples from the COVID-19 Biorepository from non-transfused patients will be assayed at two similar timepoints as Immunologic Controls.
6. Blood for immune evaluations of cellular and humoral immunity before CIP infusion (day 0) and 7, 14 and 28 days after CIP infusion. Immune testing may be done at any time if the PI determines there is a need to evaluate acute immune responses (cytokines/chemokines levels). Samples from the Prospective COVID-19 Biorepository from non-transfused patients will be assayed at two similar timepoints as Immunologic Controls.
7. "Clinical controls" will have all relevant datapoints collected via chart review (i.e. biospecimens will not be collected prospectively)

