4.2 Exclusion Criteria for Plasma Recipients

- Patients requiring mechanical ventilation or >6 liters per minute nasal cannula oxygen
- Patients on other anti-COVID-19 treatment trials (for example, those being treated with tocilizumab (anti-IL-6 receptor), Siltuximab (anti-IL-2), or Remdesivir).
- A pre-existing condition or use of a medication that, in the opinion of the site investigator, may place the individual at a substantially increased risk due to study participation
- Contraindication to transfusion or history of prior reactions to transfusion blood products.
- Medical conditions for which receipt of 500-600 mL of intravenous fluid may be dangerous to the subject (e.g., decompensated congestive heart failure).

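### As written, the 6 L/min oxygen limit is tied to nasal cannula for controls but to any supplemental oxygen for removing plasma recipients, so the two groups can differ in oxygen need

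*Combined protocol and SAP*

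**What the plan says.** Five places in the protocol set or omit an oxygen limit.

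- Section 4.2 excludes from the plasma group "Patients requiring mechanical ventilation or >6 liters per minute nasal cannula oxygen". The recipient exclusions in Section 1.0 say the same.
- Section 4.1 adds a further condition for recipients: "Patient positive for COVID-19 with respiratory symptoms within 72 hours of admission (not in ICU or on high flow oxygen". High flow oxygen is not defined, and the phrase does not appear in the recipient inclusion list in Section 1.0.
- Section 5.2.6 sets the rule between enrolment and infusion: "Subjects should be removed from the trial if they require >6L/min supplemental oxygen or mechanical ventilation prior to receiving convalescent plasma infusion".
- Section 4.3 excludes from the control group those "Requiring mechanical ventilation or >6 liters per minute nasal cannula upon admission". It has no counterpart to the high flow condition.
- The clinical control list in Section 1.0 covers floor admission with confirmed disease, age and "No receipt of convalescent plasma". It gives no oxygen or ventilation limit.

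The protocol treats devices as distinct elsewhere. The outcome measures in Section 1.0 list "nasal cannula, high flow nasal cannula, noninvasive ventilation, intubation and invasive mechanical ventilation". Face masks are not named anywhere.

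Section 7.1 matches 29 controls on gender and on age within 5 years, and on nothing else. Transfer to ICU and 28 day mortality are the primary endpoints (Section 7.3.1).

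**The concern.** Need for oxygen on the floor is plausibly one of the strongest predictors of ICU transfer. Controls are picked from charts, so whoever abstracts them will apply the criteria as written. If those criteria let in patients that the recipient rules keep out, the control group contains sicker patients by construction. Matching on gender and age does not correct this.

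The control ICU rate, and probably control mortality, would then be too high for reasons unrelated to plasma. At stake is the credibility of the comparison with matched controls that Section 2.3 promises. With 29 patients per group, a shift of one or two events is visible in that comparison.

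**Working it through.** **Step 1. The plan's own figure.** Section 9.1 states 29 evaluable patients, 80% power, 50% against 25%, two-sided 0.05, rejecting at 8 or fewer ICU admissions. The one-sample normal approximation gives

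n = [(1.960 × √(0.5 × 0.5) + 0.842 × √(0.25 × 0.75)) / 0.25]² = 28.92, so 29.

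The sample size reproduces. The exact probability of 8 or fewer of 29 is 0.0121 at 50% and 0.713 at 25%. The gap between 0.713 and 80% is a separate matter. What counts here is that the rule compares recipients with a fixed 50%. The rate observed in the 29 controls is not an input.

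**Step 2. The rules side by side, read literally.**

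| Floor patient | 4.2 (recipient exclusion) | 4.1 (recipient inclusion) | 5.2.6 (removal) | 4.3 (control exclusion) | 1.0 (control list) |
|---|---|---|---|---|---|
| >6 L/min by ordinary nasal cannula | excluded | depends on meaning of high flow oxygen | removed | excluded | accepted |
| High flow nasal cannula, >6 L/min | excluded | excluded | removed | excluded | accepted |
| >6 L/min by mask | not excluded | depends on meaning of high flow oxygen | removed | not excluded | accepted |
| Non-invasive ventilation | unclear | not stated | unclear | unclear, same term | accepted |

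The third row is where Sections 4.3 and 5.2.6 part. Whichever way Section 4.1 is read, this patient does not receive plasma: either Section 4.1 bars entry or Section 5.2.6 removes the patient before infusion. Section 4.3 accepts the same kind of patient as a control. The last column shows that Section 1.0 does not even carry the nasal cannula limit for controls.

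**Step 3. An illustration of size.** The documents do not say how many controls would be above 6 L/min by a non-cannula device, or what their ICU rate would be. All three inputs below are therefore assumptions:

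- ICU rate in such patients: 80%
- ICU rate in all other controls: 45%
- share f of such patients among controls: 5%, 10%, 20%

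Control rate = 45% + f × (80% − 45%).

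| f | Added to control rate | Extra ICU transfers in 29 |
|---|---|---|
| 5% | 0.05 × 35 = 1.75 points | 29 × 0.0175 = 0.5 |
| 10% | 0.10 × 35 = 3.5 points | 29 × 0.035 = 1.0 |
| 20% | 0.20 × 35 = 7.0 points | 29 × 0.07 = 2.0 |

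These differences would arise with no effect of plasma at all. No comparable illustration was made for mortality.

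**The case against.** Several objections carry weight.

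*Shorthand.* The number and the ventilation limb are the same in Sections 4.2, 4.3 and 5.2.6. The removal rule may simply carry the Section 4.2 limit forward to infusion in looser words. That is possible, but no section says so, and Section 1.0 separates oxygen devices. The consequence is conditional on a literal reading.

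*Section 4.1 may already exclude the mask patient.* If high flow oxygen covers masks, eligibility and removal agree. The difference from controls then remains, since Section 4.3 has no such condition.

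*Few patients may be affected.* Controls are screened on admission to a non-ICU bed, and few of them may already be above 6 L/min by mask. This stands. The upper end of the 5% to 20% range has no support in the documents.

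A reader might also infer more than the documents support:

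- *That patients on non-invasive ventilation are removed from one group and kept in the other.* Section 5.2.6 does not name non-invasive ventilation. Sections 4.2, 4.3 and 5.2.6 all use the term mechanical ventilation, so whether it covers non-invasive support is unclear in the same way for both groups.
- *That the removed patients themselves become controls.* Section 3.2 describes a comparator treated before the trial began. The point is about the kind of patient admitted to each group.
- *That the mismatch undermines the 8-of-29 decision.* An inflated control rate cannot do so. Removals could lower the recipient rate: with an overall ICU rate of 50%, 10% removed and their ICU risk at 0.7 to 1.0 (all assumed), the chance of 8 or fewer rises from 0.012 to between 0.022 and 0.048. But this counts every removal before infusion, including those on nasal cannula or ventilated. The share due to the device wording cannot be separated out.

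Timing is a further difference: controls are judged on admission, recipients up to infusion. It may well matter more. It is a separate point, and aligning the timing would leave the device wording unresolved.

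**Conclusion.** The inconsistency is on the page: one flow limit is tied to nasal cannula in some places and to any supplemental oxygen in another, recipients face an extra high flow condition, and the summary control list has no limit. On a literal reading, a floor patient above 6 L/min by mask could be barred from plasma and accepted as a control. That would favour plasma in the matched comparison of ICU transfer and mortality. It is not established that such patients will be present, or how many.

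The effect on the control ICU rate is 1.75 to 7 points, or 0.5 to 2 of 29, only under the assumed rates and shares. The size is modest, and it does not reach the fixed 50% test through the control rate. The point is still worth acting on, because the asymmetry bears on a primary endpoint and little work is needed to remove it.

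**What to change.** Reconcile Section 1.0 (including its clinical control list) with Sections 4.1, 4.2, 4.3 and 5.2.6. Use one oxygen-support definition, worded identically in each place, that states which devices count and whether non-invasive ventilation counts. Either define high flow oxygen or replace it with that definition. The limit itself is for the sponsor to decide. Apply the same definition to controls in the chart review.

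The cost is mainly wording. Section 1.0 already lists oxygen requirement at baseline, but it lists the type of support only among outcome measures, so the chart abstraction must record device as well as flow at baseline. A few control charts may drop out and need replacing.
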